The data will be analysed using descriptive statistics. This analysis will be supplemented with exploratory analysis on changes from baseline to end of extension period (Week 87) data based on MMRM analysis models similar to the main trial period data analysis, where NNC0195-0092/NNC0195-0092 and Norditropin[®] FlexPro[®]/Norditropin[®] FlexPro[®] arms will be compared. For TSQM scores the analysis will be made on Week 87 data and not change from baseline data. The interpretation of these analysis results should take into account the added complications inherent in analysing data from an extension period, including selection bias.

The NNC0195-0092 and hGH serum concentration data will be analysed using descriptive statistics. The data will also be used in the population PK analysis described in section [17.6](#).

Compliance with treatment will be evaluated based on time stamps from the ecaps in the extension period and diary data in the main trial period and the extension period. The data will be analysed using descriptive statistics.

A Kaplan-Meier plot of the time-to-withdrawal will be presented by treatment arm and the implication on the efficacy analysis of any marked differences will be commented upon in the clinical trial report.

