17.6 Population PK analysis

A population pharmacokinetic analysis (POP-PK) will be used to evaluate the effect of anti-NNC0195-0092 antibodies on the PK of NNC0195-0092. All values from samples taken 3 days after the last trial drug administration will be used for the analysis and relevant covariates that could influence the PK will be included in the analysis.

A more technical and detailed elaboration of the population pharmacokinetic analysis will be done in the modelling analysis plan (MAP) which will be finalised before the second DBL. Results will be reported in a report separate from the CTR.

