Appendix 16.1.1

~~CONFIDENTIAL~~

Date:
Version:
Status:

27 November 2017
1.0
Final

Novo Nordisk

Global and country key Novo Nordisk staff

Attachments I and II (if applicable) to the protocol are located in the Trial Master File.

Content: Global key staff and Country key staff

Protocol Amendment
no 1
to Protocol, final version 1.0
dated 25 March 2014

Trial ID: NN8640-4054

A multicentre, multinational, randomised, parallel-group, placebo-controlled (double blind) and active-controlled (open) trial to compare the efficacy and safety of once weekly dosing of NNC0195-0092 with once weekly dosing of placebo and daily Norditropin[®] FlexPro[®] in adults with growth hormone deficiency for 35 weeks, with a 53-week extension period

Trial phase: 3a

Applicable to all countries

Amendment originator:

[REDACTED]

This ~~confidential~~ document is the property of Novo Nordisk. ~~No unpublished information contained herein may be disclosed without prior written approval from Novo Nordisk. Access to this document must be restricted to relevant parties.~~

2 **Table of contents "Double click to update Table of Content"**

	Page
3	
4 1 Introduction including rationale for the protocol amendment	3
5 2 Changes to protocol version 1	6
6 3 Changes to Subject information/informed consent for version 1.....	36
7 4 Changes to Subject information/informed consent for pregnant partner version 1	42
8 5 Changes to Subject information/informed consent for male partner version 1	43

10 **1 Introduction including rationale for the protocol amendment**

11 This amendment is based on consultations with the Food and Drug Administration (FDA) in the US
12 and the Pharmaceuticals and Medical Devices Agency (PMDA) in Japan.

13

14 **1.1 The changes required by the FDA and PMDA**

- 15 • FDA: The primary analysis of the primary endpoint will be changed to an analysis based on the
16 ITT principle rather than on an assumption of missing at random. The former primary analysis
17 will be used as a secondary analysis (section 17)
- 18 • FDA: A general focus on the avoidance of missing data (sections 6, 8.2 and 8.6, introduction of
19 the SI/IC)
- 20 • FDA: Additional antibody and PK sampling will be added to align with the time points for
21 immunogenicity assessments as recommended in the FDA Immunogenicity guideline of
22 February 2013 (sections 2, 8.4.3 and 8.5.14)
- 23 • FDA: Inclusion of subjects with diabetes mellitus in order to understand the effect of the drug in

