2.1.28 Section 8.5.13 Anti-drug antibodies

Anti-drug antibodies will be assessed at randomisation and 2, 4, 8 and 16 weeks *plus 4 days (16+4d)* after randomisation and thereafter every two to three months throughout the trial ~~and at EOT~~ ~~and~~ *until the last follow-up visit* (see section 2). All samples must be drawn prior to trial drug administration if this is planned on a sampling day. Samples will be analysed *on a regular basis during the trial. The first analysis will occur after 6 months of recruitment, and then every 3 months for the remainder of the main and extension trial, with higher frequency up to all three DBLs in the trial, i.e. after 50 subjects randomised to NNC0195-0092 have completed the main trial period, after all subjects have completed the main trial period and after completion of the extension period.*

All subjects who have had ~~a~~ *two consecutive* positive antibody test result (high titre antibodies and/or persistent in vitro neutralising antibody response) will be offered an appropriate follow-up period until the antibody response has levelled out, is decreasing or until the investigator and the sponsor decide that further follow-up is not warranted. *During the trial this will be covered by the regular anti-drug antibody sampling approximately every 3 months, and after individual LSLV, the*

subjects will be requested to continue to have blood samples drawn every 3 months for follow-up analyses.

The investigator will be informed *after safety committee meeting* of any positive antibody results in case of clinically relevant impact on efficacy and/or safety. The process for assessing the impact on efficacy and safety is ~~described in~~ *performed by the safety committee* (section 12.7.1). If anti-drug antibody follow up extends beyond the LSLV of the extension period of the trial, antibody data will be collected and locked in a separate DBL once follow-up of the last subject with positive antibody test results has been completed. The results ~~may~~ *will* be reported *either* as an amendment to the Clinical Trial Report *or in a separate Clinical Trial Report*.

....

To evaluate the impact of antibody formation, results of antibody and in vitro neutralising antibody analyses will be compared to PK by collecting samples to assess serum concentrations of NNC0195-0092 at the same days as ~~for days after the last dosing and 3 days prior to~~ antibody sampling ~~takes place~~.

....

NNC0195-0092 antibodies

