(ref <http://www.cancer.gov/cancertopics/pdq/treatment/skin/Patient/page1>
and

http://www.cancer.org.au/content/pdf/HealthProfessionals/ClinicalGuidelines/Basal_cell_carcinoma_a_Squamous_cell_carcinoma_Guide_Nov_2008-Final_with_Corrigendums.pdf)

Exclusion criterion #9.

The purpose of this exclusion criterion is to ensure that subjects who have undergone surgery or have a stable adenoma can be included in the trial. This has been added to reflect the current clinical guideline practice where adenomas are subject to less follow up after 3 years with no symptoms and no growth (ref. http://press.endocrine.org/doi/abs/10.1210/jc.2010-1048?url_ver=Z39.88-2003&rfr_id=ori:rid:crossref.org&rfr_dat=cr_pub%3dpubmed).

It is important to emphasize, that subjects with a stable adenoma can only be included in the trial if they show absence of growth of the adenoma.

Exclusion criterion #12,

The criterion has been updated to reflect, that subjects who have undergone immunisation may be included in the trial.

Other changes

FDA requests that ECGs should be taken at time around the mean C_{max} . This requirement is implemented in the protocol by revising the schedule and procedures planned on visit 13 and visit 26.

The visit schedule has been updated with the option of performing IGF-I visits on day 3 as well as on day 4. This allows for more days to randomise, which will provide flexibility primarily in the titration period, but also in the treatment period.

Furthermore, we have revised text regarding database locks to correct inconsistent use of the term database lock. We will generate an interim immunogenicity report for anti-drug antibodies after 50 subjects receiving NNC0195-0092 have completed the main trial period (34 weeks of treatment),

and have actual database locks after all subjects have completed the main trial period (partial DBL) including all data for subjects completing V1a-V15, and the extension trial period (final DBL) including all data for subjects completing V1a-V29.

Finally, we have deleted redundant text regarding DXA scans to ensure that information is only stated in the relevant documents, i.e. Image Acquisition Guidelines and Site Operations Manual.

In this protocol amendment:

- Any new text is written *in italics*.
- Any text deleted from the protocol is written using ~~strike through~~.

2 Changes to protocol

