2.18 Section 8.5.9 ECG

....

ECGs will also undergo central assessment. ECG recorders will be provided to all sites. For electronic central ECG recorders and ECG evaluation vendor details, see attachment I.

Sites will be informed of the central ECG evaluation in case this evaluation reveals an abnormal ECG reading. If the abnormality, according to the investigator's judgement, represents an AE or SAE such findings should be reported by the investigator.

The ECG assessment must be performed using the provided ECG machine in the screening period, and results must be available before randomisation.

On visit 13 and visit 26 ECGs must be performed at the time around mean C_{max} , which is maximum 24 hours after dosing. Therefore, visit 13 (week 25) and visit 26 (week 64) must be planned within 24 hours after dosing (i.e. week 25 + 1 day and week 64 + 1 day).

For subjects randomised to NNC0195-0092/placebo with dosing on Mondays, Tuesdays, Wednesdays, Thursdays or Sundays, the dose must be taken as planned and visit 13 and visit 26 performed the day after dosing (see table 8-1).

For subjects randomised to NNC0195-0092/placebo with dosing on Fridays or Saturdays visit 13 and visit 26 and the previous dose must be scheduled according to table 8-1.

Table 8–1 ECG visit and dosing schedule for subjects on NNC0195-0092/placebo

Day of randomisation	Visit day in trial week 25 or 64	New dosing day in week 25 or 64
Sunday	Monday (1 day later)	NA
Monday	Tuesday	NA
Tuesday	Wednesday	NA
Wednesday	Thursday	NA
Thursday	Friday	NA
Friday	Friday	Thursday (1 day early)
	Monday (3 days later)	Sunday (2 days later)
Saturday	Monday (2 days later)	Sunday (1 day later)

For subjects randomised to Norditropin® FlexPro® the dose must be taken as planned daily and visit 13 and visit 26 scheduled according to table 8-2..

Table 8–2 ECG visit and dosing schedule for subjects on Norditropin® FlexPro®

Day of randomisation	Visit day in trial week 25 or 64	Dosing
Sunday	Monday	Daily
Monday	Tuesday	Daily
Tuesday	Wednesday	Daily
Wednesday	Thursday	Daily
Thursday	Friday	Daily
Friday	Friday	Daily
	Monday (3 days later)	Daily
Saturday	Monday (2 days later)	Daily

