2.25 Section 17.6 Population PK analysis

....

A more technical and detailed elaboration of the population pharmacokinetic analysis will be done in the modelling analysis plan (MAP) which will be finalised before the *partial second* DBL. Results will be reported in a report separate from the CTR.

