2.26 Section 27 References

27 Levin A, *Kidney International* 2013; 85, 49-61

2.27 Changes to Flow chart – section 2

+1 day visit window will be added to the IGF-I visits in the main trial and extension trial titration periods (visits 3, 5, 7, 9, 11, 16, 18, 20, 22, and 24)

ECG assessment at visits 13 and 26 will be performed at week X +1 day after dosing in stead of + 4 days from dosing as the ECG assessment should be performed at the time around the mean C_{max} , also the ECG assessment will be added to the two follow up visits 15 and 29. Furthermore ECG assessments will be deleted from the fixed dose period in both main trial and extension trial (visits 10, 12, 14, 23, 28).

Testosterone assessment for male subjects will be added to visits where biochemistry samples are collected (visits 10, 12, 13, 14, 23, 25, 26, 27, and 28), and footnote 9 will be added to the new assessments.

Correction of typing errors;

- PRO assessment: V1b is corrected to V2.
- Timing of visit for V1a: correct to V1b -1d minimum
- * added to V15 for handout of diary and training in trial drug (this should not be performed for subjects who withdraw)
- Minor typos

Footnote 9: Testosterone is assessed only in *male* subjects ~~receiving testosterone replacement therapy~~

Adding footnote:

¹⁷ V1a and V1b may be combined if site SOPs and IEC/IRB decision allow this, i.e. that patients as standard practice attend all clinic visits in a fasting state.

Protocol Amendment 6 global
Trial ID: NN8640-4054
UTN: U1111-1145-0211
EudraCT No.: 2013-002892-16

~~CONFIDENTIAL~~

Date:	26 May 2015	Novo Nordisk
Version:	1.0	
Status:	Final	
Page:	18 of 20	

¹⁸ *Visit 13 and visit 26 and the previous dose must be scheduled according to table 8-1 or table 8-2.*

Update to abbreviation list

eGFR (Estimated Glomerular Filtration Rate)

3 Changes to the informed consents

Master informed consent, version 4.0, dated 02 December 2014.

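### Section 17.6 bases the antibody-effect PK model on day-3 samples, but none of the 15 post-baseline antibody visits is on day 3

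*Protocol*

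**What the plan says.** Section 17.6 gives the population PK analysis one purpose, the effect of anti-NNC0195-0092 antibodies on PK, and one sample rule: "All values from samples taken 3 days after the last trial drug administration will be used for the analysis". Technical detail is left to a modelling analysis plan. Amendment 6 (item 2.25) edits 17.6 only to rename the database lock before which that plan is finalised. SAP version 2.0 deals with TRIM-AGHD and body weight and is silent on PK.

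Other parts of the protocol bear on that rule:

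- Section 8.5.13, as changed by Amendment 3 (item 2.1.28), compares antibody results with PK by "collecting samples to assess serum concentrations of NNC0195-0092 at the same days as" antibody sampling.
- Section 17.4.1.1 states "The NNC0195-0092 and hGH serum concentration data will be analysed using descriptive statistics". Its next sentence sends the same data to the analysis in 17.6, with no restriction on sampling day.
- Amendment 6 (item 2.18) requires that "visit 13 (week 25) and visit 26 (week 64) must be planned within 24 hours after dosing". The flow-chart item (2.27) says the ECG at these visits "will be performed at week X +1 day after dosing in stead of + 4 days from dosing".
- The introduction to Amendment 6 adds the "option of performing IGF-I visits on day 3 as well as on day 4".

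**The concern.** The day-3 rule and the antibody schedule do not meet. The visits that carry PK on day 3 are the titration IGF visits, which have no antibody sample. The visits that carry antibody samples are on other days. A modeller who follows 17.6 to the letter would set aside the concentrations drawn alongside each antibody result, and would have no exposure data from the long fixed-dose phases.

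At stake is the planned model-based answer on immunogenicity and exposure. Section 8.4.3 gives antibody-induced change as the reason for PK sampling. Amendment 1 (item 1.1) lists, among the FDA's changes, "Additional antibody and PK sampling will be added to align with the time points for" immunogenicity assessment.

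**Working it through.** **Inputs.** Weekly doses are given in weeks 0-33 and 35-86, with none in weeks 34 and 87 (Section 5.3). Antibody samples are drawn before any dose due that day (8.5.13). Visit times come from the flow charts, with V13 and V26 at day 1 after dosing under Amendment 6. The extracted flow-chart tables are not clean, so the antibody rows were read across Table 2-2 and the marked-up tables in Amendment 1.

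**Formula.** Days since last dose = visit day minus the latest dose day before it.

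| Antibody visits | Visit day minus last dose day | Days since dose | Protocol 2.0 |
|---|---|---|---|
| V4, V6, V10 | 14-7, 28-21, 56-49 | 7 | 7 |
| V17, V19, V23 | 259-252, 273-266, 301-294 | 7 | 7 |
| V12, V14 | 116-112, 235-231 | 4 | 4 |
| V25, V27, V28 | 375-371, 529-525, 606-602 | 4 | 4 |
| V13, V26 | 176-175, 449-448 | 1 | 4 |
| V15, V29 | 245-231, 616-602 | 14 | 14 |

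Day-3 count: 0 of 15 after Amendment 6 and 0 of 15 under protocol 2.0.

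**Windows.** These do not rescue the count. V12, V25 and V27 move by whole weeks, V13 and V26 are tied to the dose, and V14 and V28 have +2 days (day 4 to 6).

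**Where day-3 PK exists.** It exists at V3, V5, V7, V9, V11 (days 10, 24, 38, 52, 66) and V16, V18, V20, V22, V24 (days 255, 269, 283, 297, 311). None carries an antibody sample. Amendment 6 lets each slip to day 4, which a literal rule would also exclude.

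**Time after the last day-3 sample.**

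- Main period: 238-66 = 172 of 238 days (72%).
- Extension: 609-311 = 298 of 609-245 = 364 days (82%).
- Section 5.3.5 allows two 2-week postponements in each titration period. V11 could then fall on day 94 and V24 on day 339, still before the earliest V12 (116-7 = 109) and V25 (375-7 = 368).

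**Distance from each antibody visit to the nearest earlier day-3 PK.**

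- V4, V6, V10, V17, V19, V23: 4 days.
- V12, V13, V14, V15: 50, 110, 169, 179 days (from V11).
- V25, V26, V27, V28, V29: 64, 138, 218, 295, 305 days (from V24).

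**Next day-3 PK after a late first detection.** From V12, V13, V14 or V15 it is V16, at 255-116 = 139, 255-176 = 79, 255-235 = 20 or 255-245 = 10 days. From V25-V29 there is none. So 9 of 15 antibody visits have no day-3 sample at or after them in their own period.

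**The case against.** The best defence is textual. Section 17.6 says the day-3 values will be used; it does not say that only they will be. Section 17.4.1.1 passes the concentration data to 17.6 without a day limit. The deciding document, the modelling analysis plan, was not supplied. The sentence also looks like a leftover: Amendment 1 struck a reference to a single sample 3 days after dosing from 8.4.3, and its mark-up moves the main-period fixed-dose visits from +3d to +4d, while 17.6 kept the old day. All of this stands. It makes the exclusion conditional, but it does not make the sentence fit the schedule, since 17.6 names no other sample.

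A reader might go further in four ways that the documents do not support.

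- *Amendment 6 caused the mismatch.* It did not. The count was zero before, and only V13 and V26 moved.
- *The paired PK is otherwise unused.* Amended 8.5.13 compares same-day PK with antibody and neutralising results. The treatment discontinuation rule for neutralising antibodies uses influence on PK, and PK is analysed for relevant subjects to support the ad hoc safety group.
- *The model must show no effect whatever the truth.* Section 17.6 sets no cut-off at the end of the main period. Persistent antibodies first seen at V12-V15 could act on V16-V24 in subjects who continue on NNC0195-0092, and an antibody first detected at V12 may have begun before V11. At the six titration antibody visits, a day-3 sample four days earlier can still be linked to antibody status.
- *The dilution of the effect can be given a number.* That would need an assumed change in exposure and an assumed covariate form, and the documents give neither.

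**Conclusion.** The point holds as a conflict between one sentence and the schedule. Read literally, 17.6 omits all of the scheduled same-day antibody and PK pairs (0 of 15 on day 3) and has no day-3 PK after V11 in the main period or V24 in the extension. Late main-period antibodies would be assessed only through V16-V24, and antibodies arising after V24 not at all in this model. Titration-phase linkage and the individual assessments under 8.5.13 and by the safety committee remain.

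This rests on nominal weekly dosing, on the antibody visits as read from imperfectly extracted tables, and on the literal reading of 17.6. A withdrawal visit could by chance fall on day 3. If the modelling analysis plan already uses every sample, only the protocol wording needs correcting. The primary, key secondary and adverse event analyses are untouched, and the population PK results are reported separately from the trial report.

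**What to change.** Replace the 3-day sentence in 17.6, and align the modelling analysis plan before the partial database lock. Suggested text: all available post-dose NNC0195-0092 concentrations will be used with actual time since last dose, and antibody status will be a time-varying covariate. Dose dates and times are already recorded in the diary (Section 8.3.5). Take antibody status from the same-day sample and carry it forward to the IGF visits.

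Widening the rule to days 3-4 is not enough. It would recover at most five antibody visits (V12, V14, V25, V27, V28) and still drop V13 and V26 (day 1), V15 and V29 (day 14) and the six samples at day 7.

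The cost is wording. The ECG timing and the sampling schedule can stay, and no visit, sample or assay is added provided PK is drawn on each antibody day as amended 8.5.13 says. That should be confirmed for V26 and V27, where the PK row of the extension flow chart marked up in Amendment 1 appears blank.

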17.7 Health economics and/or subject reported outcomes

Please refer to [17.4.1.1](#). Results from the PROs will be reported in the CTRs.

18 Ethics

Please refer to section [3.1.5](#) for a description of the risks and benefits.

18.1 Informed consent

In seeking and documenting informed consent, the investigator must comply with applicable regulatory requirement(s) and adhere to ICH GCP¹ and the requirements in the Declaration of Helsinki².

Before any trial-related activity, the investigator must give the subject verbal and written information about the trial and the procedures involved in a form that the subject can read and understand.

The subjects must be fully informed of their rights and responsibilities while participating in the trial as well as possible disadvantages of being treated with the trial products.

The investigator must ensure the subject ample time to come to a decision whether or not to participate in the trial.

A voluntary, signed and personally dated informed consent must be obtained from the subject before any trial-related activity.

The responsibility for seeking informed consent must remain with the investigator, but the task may be delegated by the investigator to a medically qualified person, in accordance with local requirements. The written informed consent must be signed and personally dated by the person who seeks the informed consent before any trial-related activity.

If information becomes available that may be relevant to the subject's willingness to continue participating in the trial, the investigator must inform the subject in a timely manner, and a revised written subject information must be provided and a new informed consent must be obtained.

18.2 Data handling

If the subject is withdrawn from the trial or lost to follow-up, then the subject's data will be handled as follows:

- Data already collected and data collected at the end-of-trial and follow up visits will be retained by Novo Nordisk, entered into the database and used for the trial report.
- Safety events will be reported to Novo Nordisk and regulatory authorities according to local/national requirements.

If data is used, it will always be in accordance with local regulations and IRBs/IECs.

